Part 1: Some patients will have an insertable FDA/CE cardiac rhythm monitor and pulmonary artery pressure monitor that captures cardiopulmonary haemodynamics and daily activity. These patients will be provided with a remote monitoring system to capture daily blood pressure, oxygen saturations and body weight. This permits remote monitoring with the option to attend the hospital, as required. The patients without a monitor will attend their specialist hospital site for a baseline assessment (inclusive of a right heart catheterisation, RHC),

and then again at the end of Week 4 to assess tolerability, with telephone assessments at the end of Weeks 1, 2 and 3.

The first patient will receive Imatinib 100mg (x1) once daily. Subsequent patients will enter the trial at no less than 4 week intervals and receive a dose of Imatinib (up to 400mg) based on the experience of the previous patient(s) at 4 weeks, using a statistical model to identify the most likely highest tolerated dose. By definition, the highest tolerated dose is reached in this trial when there is a 20% probability that a patient will not be able to continue the drug for 5 consecutive days.

All patients who are tolerating Imatinib will be asked to continue on their assigned dose to the end of week 24 and their clinical response will be measured by the change in PVR (measured using the implanted monitor or, where a patient does not have a monitor by RHC).

Part 2: All patients will receive the highest tolerated dose (defined in Part 1) for 24 weeks. Patients will be recruited as suitable (i.e. there is no staggering) and monitored for safety at the end of Weeks 4, 8, 12 and 24, with telephone assessments at the end of Weeks 16, 20 and 28. Clinical response will be measured by change in PVR from baseline at Week 24. The primary efficacy endpoint is a binary variable: for patients with a baseline PVR >1000 dynes·s·cm⁻⁵, success is defined by an absolute reduction in PVR of ≥300 dynes·s·cm⁻⁵ at 24 weeks; for patients with a baseline PVR ≤1000 dynes·s·cm⁻⁵, success is a 30% reduction in PVR at 24 weeks.

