Some patients with PAH attending the specialist clinics have both an implanted cardiopulmonary monitor and an activity monitor that permits remote sensing and a remote system for provision of daily blood pressure, oxygen saturations and body weight. These offer a particular advantage in a time of Covid-19, minimising contact with the hospital. The monitoring also offers greater oversight of the patient and closer safety monitoring. Remotely acquired patient data are reviewed twice a week via a central clinical team based in Sheffield. Many of these patients would be suitable for Part 1 of this study where the emphasis is on identifying a tolerated dose. These patients would not require a baseline RHC, as key data would be retrieved from the implanted monitor. Relevant data will be sent as de-identifiable information to the recruiting site for upload onto the study database (eCRF). Continuous monitoring data can be sent to Imperial College London (upon request) as pseudonymised (coded) data for consideration of the Trial Steering and Data Monitoring Committees, if there are any concerns regarding patients' safety. Follow-up would be scheduled by telephone or video conferencing with hospital visits being optional. Participants who consent to take part but do not have an implanted cardiac monitor will attend the hospital for a baseline RHC and then again at the end of Week 4 after starting Imatinib to assess tolerability, with telephone or video conference assessments at the end of Weeks 1, 2 and 3.

We will explore 4 doses between 100mg and 400mg of Imatinib (100mg, 200mg, 300mg and 400mg), the maximum dose escalation between patients is limited to 100mg to protect against rapid escalation to an intolerable dose. The first patient will receive Imatinib 100mg (x1) once daily. Subsequent patients will enter the trial at no less than 4 week intervals. The second patient will receive a dose of Imatinib based on the experience of the previous patient(s) at 4 weeks; if 100mg is tolerated, the second patient will receive 200mg. The third patient will receive a dose of Imatinib based on the experience of the previous patients at 4 weeks, using a statistical model to identify the most likely highest tolerated dose. This will be between 100mg and 300mg daily. The statistical model will be used to choose the dose for the fourth patient up to a maximum of 400mg daily.

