By definition, the highest tolerated dose is reached in this trial when there is a 20% probability that a patient will not be able to continue the drug for 5 consecutive days. All patients who are tolerating Imatinib will be asked to continue on their assigned dose to the end of week 24 and their clinical

response will be measured by the change in PVR (measured through a follow-up RHC). Dose adjustments within the range 100mg to 400mg daily are permitted at the discretion of the responsible physician according to clinical need but if a patient is unable to tolerate 100mg daily, they are withdrawn from the study.

The objective of Part 2 is to define the clinical response to Imatinib after 24 weeks treatment with the highest tolerated dose by measuring the change in PVR through a follow-up RHC. Some patients from Part 1 will have continued on the highest tolerated dose to 24 weeks and so be evaluable for additional efficacy at this dose. Part 2 will continue recruitment of additional patients to a total of 34 evaluable patients; all patients in Part 2 will receive the highest tolerated dose (defined in Part 1) for 24 weeks. Patients will be monitored for safety at the end of Weeks 4, 8, 12 and 24, with telephone assessments at the end of Weeks 16, 20, and 28. If a patient becomes intolerant of Imatinib, they will be allowed to continue with a reduced dose or alterative treatment as guided by their NHS specialist physician, but they will be withdrawn from the study. Beyond that point, we will not be collecting new data from those patients. The clinical response of all patients who complete 24 weeks on the highest tolerated dose of Imatinib will be measured by change in PVR from baseline at Week 24. The primary efficacy endpoint is a binary variable: for patients with a baseline PVR >1000 dynes·s·cm⁻⁵, success is defined by an absolute reduction in PVR of ≥300 dynes·s·cm⁻⁵at 24 weeks; for patients with a baseline PVR ≤1000 dynes·s·cm⁻⁵, success is a 30% reduction in PVR at 24 weeks.

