4.3 Selection of study population

Patients participating in this study are adult males and females with symptomatic PAH as defined by the eligibility criteria below. No deviations will be made to the eligibility criteria.

PAH is a rare condition. Patients with PAH attend one of 8 UK specialist centres in the UK for diagnosis and management decisions. Currently these centres have recruited over 650 patients with well-defined PAH to a cohort study. These patients are in regular follow-up and have been consented to recall to future clinical studies. We anticipate recruiting 1 to 2 patients per month. This is based on a recent academic-led study of tocilizumab in PAH and the expertise of the recruiting centres in clinical studies in PAH.

The Covid-19 pandemic has changed clinical practice, with many more consultations taking place by telephone or video conferencing. This is facilitated by the use of remote monitoring − See Figure 5. The PAH cohort has an expanding number of patients with an implanted CardioMEMS[™] Heart Failure system and a Fitbit activity monitor as part of the FIT-PH study (Feasibility of Novel Clinical Trial Infrastructure, Design and Technology for Early Phase Studies in Patients with Pulmonary Hypertension; Ethics approval 19/YH/0354). These have been under follow-up for a mean of 7 months and are stable.

This patient group provide daily data about their health (level of physical activity, day and night cardiac rate and rhythm, heart rate variability, thoracic impedance, respiratory rate, systemic blood pressure, oxygen saturations, body weight, pulmonary artery pressure, cardiac output and stroke volume) to a hospital-based monitoring team and benefit from close contact with the specialist team while reducing travel to the hospital. Remote systemic blood pressure, oxygen saturations and body weight are provided through the FDA/CE approved Cordella Heart Failure System (24). The protocol of the FIT-PH study observational study permits evaluation of therapeutic interventions. This group of patients would be suitable for assessing the tolerability of Imatinib in Part 1 of the PIPAH study. They can provide valuable additional information on the haemodynamic response to Imatinib that cannot be obtained by other means as well as objective activity data to enable interpretation of self-reported information.

[figure not shown]

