4.3.1 Inclusion criteria

- 1. Subjects aged between 18-80 years old
- **2.** PAH which is idiopathic; PAH heritable; PAH associated with connective tissue disease; PAH after ≥1 year repair of congenital systemic to pulmonary shunt; or PAH associated with anorexigens or other drugs
- 3. Subjects willing to be genotyped for genes that influence PDGF activity
- **4.** Resting mean pulmonary artery pressure ≥25 mmHg, Pulmonary capillary wedge pressure ≤15 mmHg, PVR >5 wood units, and normal or reduced cardiac output, as measured by right heart catheterisation (RHC) at entry
- **5.** Six-minute walking distance >50m at entry
- **6.** Stable on an unchanged PAH therapeutic regime comprising at least 2 therapies licensed for PAH (any combination of endothelin receptor antagonist, phosphodiesterase inhibitor or prostacyclin analogue) for at least 1 month prior to screening
- 7. Able to provide written informed consent prior to any study mandated procedures
- **8.** Contraception: Women of childbearing potential are eligible to participate after a negative highly sensitive pregnancy test if they are taking a highly effective method of contraception during treatment and until the end of relevant systemic exposure.

Fertile males who make use of condom and contraception methods during treatment and until the end of relevant systemic exposure in women of childbearing potential.

Women of childbearing potential and fertile men* are eligible to participate, if they agree to use highly effective contraceptive methods with typical-use failure rate <1% per year, when used consistently and correctly. Such methods include:

- sexual abstinence
- combined (oestrogen and progestogen containing) hormonal contraception associated with inhibition of ovulation¹:
 - o oral
 - o intravaginal
 - o transdermal
- progestogen-only hormonal contraception associated with inhibition of ovulation1:
 - o oral
 - o injectable
 - o implantable²
- intrauterine device (also called IUD)²
- intrauterine hormone-releasing system (also known as IUS)²
- bilateral tubal occlusion²
- vasectomised partner^{2,3}

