6.11 End of treatment assessment (Week 24 ± 3 days)

The patient will be invited to attend their local hospital at the end of Week 24 (or earlier if early termination of imatinib) in order to undergo the following procedures (in the case of patients with an implanted CardioMEMSTM device, a home assessment will be offered):

- Physical examination
- Concomitant medications
- Document AEs
- Vital signs: (i) Resting supine BP, (ii) pulse measurement, (iii) temperature, (iv) pulse oximetry (incl. respiratory rate), and (v) weight
- ECG
- WHO Functional Class
- 6MWT and Borg dyspnoea index
- Right heart catheterisation*(unless the patient has an implanted CardioMEMS™ device)
- Echocardiogram
- QoL questionnaire
- Blood samples for haematology and clinical chemistry, and serum pregnancy test whereas indicated (for women of childbearing potential)
- Blood sample for Imatinib levels
- · Research blood sampling

Review of the diary, Imatinib collection and reconciliation
 *can be performed on a separate day ± 3 days apart from the original visit date, as needed.

6.12 Follow-up telephone assessment (Week 28, or 4 weeks after early termination ± 3 days)

At the end of the study, clinical follow-up will continue via the local NHS-designated pulmonary hypertension clinics. The patients that have completed the 24-week treatment period on Imatinib may continue with the study drug under the supervision of their local NHS specialist physician. Those who discontinue Imatinib will be reviewed by their local physician for alternative treatment. In all cases, patients will receive a telephone call from the study physician/clinical study team once they have been off study drug for 4 weeks (±3 days) to check concomitant medications, and for the occurrence of AEs. Patients will be also asked to weigh themselves and report their weight and ankle swelling. For women of childbearing potential: A urine pregnancy test will be performed at home. A telephone call will be performed within 72 hours of the urine test date to enquire about the results.

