7.10 Right heart catheterisation (RHC)

RHC will be conducted at screening (Visit 1) and at the end of Week 24 in patients who do not have an implanted CardioMEMS™ device. The RHC at baseline can be omitted as long as the patient had one within a

^{*}for women of childbearing potential

month prior to screening for reasons not related to the study (e.g. for clinical purposes). On this occasion, retrospective RHC data (up to one month old) can be used for both the screening and baseline RHC entries. A qualified physician will be responsible for interpreting the RHC results. Any RHC finding that is judged by the site investigator as a clinically significant change (worsening) will be considered an Adverse Event. In a RHC procedure the catheter passes through the veins to the right side of the heart. Fluoroscopic X-ray images are used to guide the tip of the catheter up to the heart. A special type of dye called contrast medium is injected through the catheter and X-ray images (angiograms) are taken. The contrast medium is visible on the angiograms, showing the blood vessels that the contrast travels through and clearly highlights any blood vessels that are narrowed or blocked.

The amount of radiation used during the procedure depends on the complexity of the procedure but is approximately equivalent to about 7mSv effective dose, which is equivalent to about 3 years of natural background radiation. The maximum total radiation dose from the CT head scan (see above) and RHC procedures involved in this study is about 16 mSv. This is equivalent to approximately 7 years of natural background (2.3mSv/year) radiation. The risk of developing cancer as a consequence of taking part in this study is about 0.08 % (1 in 1250), which is low. For comparison, the natural lifetime cancer incidence in the general population is about 50%.

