7.11 Remote monitoring and management system of haemodynamic data

The CardioMEMS™ Heart Failure System (27) provides pulmonary artery hemodynamic data used for monitoring and management of Heart Failure patients. The system includes an implantable wireless sensor with delivery catheter, a remote monitoring electronics system, and a System database.

The wireless sensor is implanted into the distal pulmonary artery. Once implanted, the CardioMEMS Pulmonary Artery Sensor provides non-invasive hemodynamic data that is collected in the System database. The dataset includes details on the pulmonary artery pressure waveform, systolic, diastolic, and mean pulmonary artery pressure and cardia rhythm (heart rate). This hemodynamic data is transferred online to a secure website that serves as the System database, so that monitoring information is available at all times.

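### For patients with an implanted monitor the protocol contradicts itself on how PVR is measured, and the listed monitor data lack the wedge pressure that PVR needs, so a different quantity could enter the primary count

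*Protocol*

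**What the plan says.** **Source of PVR.** The Study Summary (Treatment, Part 1) says that clinical response is "measured by the change in PVR (measured using the implanted monitor or, where a patient does not have a monitor by RHC". Protocol section 4.1, on the same Part 1 patients, says their "response will be measured by the change in PVR (measured through a follow-up RHC", with no exception for monitor patients.

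**RHC waiver.** Section 4.1 also says of monitor patients: "These patients would not require a baseline RHC, as key data would be retrieved from the implanted monitor". Section 6.2 waives the baseline RHC for them. Section 6.11 waives it at Week 24 ("unless the patient has an implanted CardioMEMS™ device"), and section 7.10 schedules it "at the end of Week 24 in patients who do not have an implanted CardioMEMS™ device". Appendix 1 repeats the exemption in a footnote. None of these waivers is limited to Part 1.

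**Entry.** Inclusion criterion 4 (section 4.3.1 and Study Summary) sets a wedge pressure limit of 15 mmHg and requires "PVR >5 wood units, and normal or reduced cardiac output, as measured by right heart catheterisation (RHC) at entry". It has no device exception, and section 4.3 allows no deviations from eligibility.

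**Monitor data.** Section 7.11: "The dataset includes details on the pulmonary artery pressure waveform, systolic, diastolic, and mean pulmonary artery pressure and cardia rhythm (heart rate". Section 4.3 gives a wider list, ending "body weight, pulmonary artery pressure, cardiac output and stroke volume) to a hospital-based monitoring team". Neither list contains a wedge pressure.

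**Who is counted.** The Study Summary and section 4.1 let Part 1 patients be evaluated in Part 2 if they finish the 24-week course at the dose selected in Part 1. Section 10 stops the trial at 1 or no responses in 13 and rejects the null at 7 or more in 34.

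**The concern.** The primary endpoint applies sharp cut-offs to PVR. Above a baseline of 1000 dynes·s·cm⁻⁵, success is an absolute fall of at least 300. At or below 1000, it is a 30% fall. PVR is mean pulmonary artery pressure minus wedge pressure, divided by cardiac output. Without a wedge pressure, the nearest quantity that the listed monitor data support is total pulmonary resistance, which omits the subtraction. It is always higher than PVR, so it can also move a patient from one success rule to the other.

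A site cannot follow both section 4.1 (follow-up RHC) and the Week 24 waiver. If section 4.1 governed at Week 24 while baseline stayed on the monitor, the change would be taken between two different methods. With decision bounds of 2 in 13 and 7 in 34, a few reclassified patients can decide the trial.

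**Working it through.** **1. The plan's own design figures.** Section 10 gives null rate 0.10, alternative 0.27, 13 patients then 21 more, stop at 1 or fewer, reject at 7 or more.

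- Early termination under the null: 0.9^13 + 13 × 0.1 × 0.9^12 = 0.2542 + 0.3672 = 0.6213.
- Expected size: 13 + (1 − 0.6213) × 21 = 20.95.
- Rejection probability: the sum over x = 2 to 13 of P(X1 = x) × P(X2 ≥ 7 − x), with X1 ~ Bin(13, p) and X2 ~ Bin(21, p). This gives 0.0420 at p = 0.10 and 0.8034 at p = 0.27.

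All four agree with the protocol, so the design arithmetic is not at issue.

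**2. Can the listed data give PVR?** PVR = 80 × (mPAP − wedge) / CO.

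| Input | Section 7.11 | Section 4.3 | RHC |
|---|---|---|---|
| mPAP | yes | pulmonary artery pressure | waived |
| CO | no | yes | waived |
| Wedge | no | no | waived |

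The protocol gives no formula, surrogate or carried-forward wedge, and schedules no wedge at Week 24 for these patients.

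**3. Does it change responder status?** The haemodynamic values below are assumed (mPAP/wedge/CO), with the wedge held constant. Total resistance = 80 × mPAP / CO.

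- *56/8/4.0 to 47/8/4.6.* PVR: 80 × 48/4.0 = 960, then 80 × 39/4.6 = 678. The fall is 29.3% under the 30% rule: failure. Total resistance: 80 × 56/4.0 = 1120, then 80 × 47/4.6 = 817. The baseline now exceeds 1000 and the fall is 303: success.
- *50/10/4.5 to 42/10/5.2.* PVR: 80 × 40/4.5 = 711, then 80 × 32/5.2 = 492. The fall is 30.8%: success. Total resistance: 80 × 50/4.5 = 889, then 80 × 42/5.2 = 646. The fall is 27.3%: failure.

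**4. Mixed methods.** Suppose baseline were total resistance from the monitor and Week 24 were PVR by RHC. A patient unchanged at 50/10/4.5 would go from 889 to 711, an apparent fall of 178/889 = 20%. Success would need a Week 24 value of 0.70 × 889 = 622, which is a true PVR fall of only 1 − 622/711 = 12.5%.

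**5. Effect on the error rates.** The sum in step 1 was repeated with k of the 13 stage 1 patients given a different success probability q and all others kept at 0.10. Both k and q are assumed; the documents give neither.

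| Type I error | q = 0.05 | 0.10 | 0.15 | 0.20 |
|---|---|---|---|---|
| k = 4 | 0.030 | 0.042 | 0.056 | 0.072 |
| k = 6 | 0.024 | 0.042 | 0.064 | 0.091 |

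If monitor patients succeed at 0.20 instead of 0.27 under the alternative, power falls from 0.803 to 0.763 (k = 4) or 0.740 (k = 6).

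**The case against.** Four stronger readings are tempting, and the documents do not carry them.

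- **That PVR cannot be had at all, or that eligibility cannot be checked.** Criterion 4 requires an RHC wedge at entry, and sections 6.2 and 7.10 accept an outside RHC from within a month before screening. The list in section 7.11 is not declared exhaustive, and section 4.1 speaks of unspecified key data. An entry wedge may therefore exist and could be borrowed. The protocol does not say so, however, and a borrowed value would leave Week 24 without a measured wedge. Section 4.3 puts the monitor patients at a mean of 7 months of follow-up, so a catheterisation done around implantation would generally fall outside the one-month allowance.
- **That the four extension patients could supply 4 of the 7 responses.** Section 10 doses them at or below the selected dose to inform a harm-benefit assessment and does not say that they enter Part 2. Only discordant patients distort the count in any case.
- **That the two measures diverge widely.** Larger gaps appear if the wedge is assumed to shift between visits, but nothing in the documents supports a particular shift. With a constant wedge, the discordant cases in step 3 lie close to the cut-offs.
- **That the trial result becomes uninterpretable.** The error rates in step 5 move materially but do not lose their meaning.

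It is also fair that section 4.1 names a follow-up RHC for Part 2. That helps only if it overrides the waivers, which are written without reference to Part. Excluding monitor patients is not the only remedy: stating and justifying a derivation, or requiring RHC for patients who are counted, would also answer the point.

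**Conclusion.** The contradiction is certain on the text. Two passages name different sources of PVR for the same patients, the waivers conflict with one of them and with the entry criterion, and the listed monitor data cannot yield PVR as the primary endpoint uses it. That total resistance would actually be used is an inference; no passage says so. The number of affected patients is not given.

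The size of the effect therefore rests on assumptions. With 4 monitor-based stage 1 patients, type I error runs from 0.030 to 0.072 against the stated 0.042 as their assumed null success rate runs from 0.05 to 0.20. The supported conclusion is that the stated error rates are no longer assured. This should be corrected before the interim count, because deciding afterwards which patients count would be data-dependent.

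**What to change.** 1. State in sections 3.1, 4.1 and 10, before the interim count, that the primary response count (the 13 and the 34) includes only patients scheduled for PVR by RHC at both baseline and Week 24. Defining this by schedule rather than by availability keeps drop-outs in the denominator, in line with the intention-to-treat analysis in section 10.
2. Report monitor-only patients separately, as change in mean pulmonary artery pressure or total pulmonary resistance, under that name.
3. State that the RHC waiver does not apply to patients enrolled in Part 2. Otherwise a Part 2 device patient could never be scored under item 1.
4. Reconcile the Study Summary (Treatment, Part 1, and inclusion criterion 4) with sections 4.1, 4.3.1, 6.2, 6.11, 7.10 and Appendix 1.

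**Cost.** The change is one of wording, but fewer Part 1 patients carry over and each must be replaced. At the 1 to 2 recruits per month expected in section 4.3, four patients (an assumed number) would take 4/2 = 2 to 4/1 = 4 months. Any device patient enrolled in Part 2 would undergo RHC. The Study Summary already describes Part 2 as recruiting a separate group of up to 34, so the change fits the stated plan.
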